#### 5.4.2 Analysis of Overall Survival

OS will be summarized, estimated and plotting using Kaplan-Meier method on the FAS for HCC subjects. Time of death will be censored for subjects who are without death information at the time of OS analysis. Censoring rules for OS are specified in Table 6.

**Table 6 Censoring Rules for Overall Survival Endpoint**

Situation	Event Date or Censoring	Outcome
Death during study	Date of death	Death
Death after data cut-off	Date of data cut-off	Censored
Subject still alive at data cut-off	Date of data cut-off	Censored
Subject lost to follow-up before data cut-off	Date last known to be alive	Censored

A listing of PFS and OS will be provided.

### 5.5 PHARMACOKINETIC, PHARMACODYNAMIC, PHARMACOGENOMIC, AND OTHER BIOMARKERS ANALYSES

#### Pharmacokinetic Analysis

Plasma concentrations of H3B-6527 will be tabulated and summarized by dose level, day, and time. H3B-6527 PK parameters will be derived from plasma concentrations by noncompartmental analysis using actual times. Minimally, the following PK parameters will be calculated:  $C_{max}$ ,  $t_{max}$ ,  $AUC_{(0-t)}$ , accumulation ratio ( $R_{acc}$ ); and if data permit, area under the plasma concentration-time curve extrapolated to infinity ( $AUC_{(0-inf)}$ ), terminal elimination half-life ( $t_{1/2}$ ), apparent total body clearance (CL/F), and apparent volume of distribution during the terminal phase ( $V_z/F$ ). More details will be described in a separate PK analysis plan.

Pharmacodynamics, Pharmacogenetics (PG) and other biomarker analyses will be performed and reported separately. Details of these analyses will be described in separate analysis plans.

## 5.6 Safety Analyses

All safety analyses will be performed on the Safety Analysis Set and “as treated” basis except the evaluation of DLT and determination of the MTD. The number (percentage) of DLT will be summarized on and the determination of the MTD will be based on DLT Analysis Set in the Dose Escalation part.

Subjects who do not receive study drug for at least 17 of 21 days (80%; not necessarily consecutively) during the first cycle for reasons not considered to be a DLT by both the investigators and the Sponsor will be replaced. The subjects who are replaced will not be considered evaluable for DLT assessments.

Safety data include all AEs, SAEs, clinical laboratory tests, vital signs, ECGs, MUGA/echocardiogram, and ophthalmic examinations.

Safety parameters will be summarized using descriptive statistics (mean, standard deviation, median, Q1, Q3, and range for continuous variables; numbers and percentages for categorical measures).

The effects of H3B-6527 on cardiovascular repolarization will be evaluated via 12-lead continuous cardiac Holter monitoring around first dose administration on C1 Day 1 and Day 8 in the dose escalation part of the study only. Individual ECGs will be extracted from the Holter recordings at specified time points per ECG manual and will be evaluated by a central laboratory. QT intervals will be measured from Lead II and will be corrected for heart rate (QTc) using Fredericia’s (QTcF) correction factors. The primary QTc parameter will be QTcF; secondary parameters (QTc corrected using Bazett’s formula [QTcB], QT, QRS, PR, and heart rate) and wave forms (T waves) will be evaluated.

### 5.6.1 Extent of Exposure

The extent of exposure of study drug will be summarized for the Safety Analysis Set by number of cycles/days on treatment, duration of treatment, total dose, the number of cycles received and the number of subjects requiring dose reductions, treatment delay and treatment discontinuation due to AEs. A subject listing of study drug administration by cycle/visit will be provided.

The treatment compliance will be summarized for the Safety Analysis Set by dose intensity and received dose as percentage of planned starting dose.

Duration of treatment (days) = last dose date of study drug – first dose date of study drug +1.

Dose intensity (mg/day) = total dose received during the study / (duration of treatment in days)

Received dose as percentage of planned starting dose (%) =  $100 \times$  dose intensity (mg/day) / planned starting dose (mg/day).

Listings of study drug administration by cycle/visit and treatment exposure will be provided.

## 5.6.2 Adverse Events

The AE verbatim descriptions (investigator terms from the CRF) will be classified into standardized medical terminology using MedDRA. AEs will be coded to the MedDRA (Version 19.0 or higher) lower level term (LLT) closest to the verbatim term. The linked MedDRA preferred term (PT) and primary system organ class (SOC) are also captured in the database.

A treatment-emergent adverse event (TEAE) is defined as an AE that emerges during treatment up to 28 days after last dose, having been absent before treatment or:

- reemerges during treatment, having been present before treatment but stopped before treatment, or
- worsens in severity during treatment relative to before treatment state, when the AE was continuous.

Only TEAEs will be included in summary tables.

The incidence of TEAEs will be reported as the number (percentage) of subjects with TEAEs by SOC and PT. A subject will be counted only once within a SOC and PT, even if the subject experienced more than one TEAE within a specific SOC and PT. The number (percentage) of subjects with TEAEs will also be summarized by highest CTCAE grade.

The number (percentage) of subjects with TEAEs, the number (percentage) of subjects with TEAEs leading to death, the number (percentage) of subjects with SAEs, and the number (percentage) of subjects with TEAEs leading to discontinuation from study drug will be summarized by MedDRA SOC and PT.

Also, the TEAEs will be summarized by relationship to study drug (Yes or No) and by CTCAE grade.

To assess the MTD and DLT, the number (percentage) of subjects with DLT events in each dose level will be summarized.

All AEs will be presented in subject data listings. In addition, listings of DLTs, SAEs, AEs leading to death and AEs leading to discontinuation from study drug will be provided.

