Due to the potential for dropouts during the first cycle of treatment (eg, because of early disease progression), a cohort may initially be expanded to include up to 2 additional subjects. However, if these additional subjects are to be enrolled, they must start treatment ≤ 14 days after the third subject enrolled in the cohort was first dosed with H3B-6527. The decision to dose escalate may still be made after the third subject enrolled to the dose level in question has completed the first cycle of treatment. However, if under these circumstances the decision is made to enroll subjects to a higher dose level, and one of the additional subjects treated at the preceding dose level experiences a DLT in the first cycle of treatment, then further enrollment of subjects to the higher dose level will be suspended until it can be determined whether the preceding dose level exceeds the MTD. In the meantime, subjects enrolled to the higher dose level may continue treatment at that dose if they are tolerating it well, and if continuing treatment is considered appropriate for the toxicity in question.

For dose escalation purposes, toxicities assigned as DLTs during the first cycle will be assessed. After 3-6 subjects in a cohort have completed Cycle (C) 1, all available safety data will be reviewed by the SRC, consisting of Sponsor personnel and investigators, and the decision to proceed to the next dose cohort will be made jointly. If different dose schedules are explored, decisions regarding dose escalation will be made based on review of data from subjects enrolled in cohorts on the same schedule, however, safety data from alternate schedules may be considered by the SRC. Toxicities will be graded using the National Cancer Institute Common Terminology Criteria for Adverse Events ([CTCAE](#)), Version 4.03.

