Once a subject has completed C3 at the initially assigned dose schedule and dose level (QD or BID), intrapatient dose escalation will be allowed. Only subjects who have not progressed on treatment and did not have a dose reduction or interruption because of a drug-related AE, will be permitted to escalate to the highest dose level that has completed DLT assessment within that dose schedule and has been shown to be safe (no DLT in the first 3 subjects or no more than 1 DLT in 6 subjects). Subjects on the intrapatient dose escalation will not be included in the DLT analysis at the higher dose level. The investigator and the medical monitor must agree that dose escalation is appropriate for the subject prior to escalating their H3B-6527 dose level.

The starting dose of 300 mg QD (first-in-human dose) is the HED of 1/6th the HNSTD in dog. Dose escalation will follow a modified Fibonacci design such that the magnitude of the escalation will decrease as the dose level nears the HED of the HNSTD in dogs (HED \approx 2000 mg).

Table 1 Dose Cohorts in H3B-6527 Dose-Escalation

Dose Level	Initial No. of Subjects	H3B-6527 Total Daily Dose
-1	3	150 mg
1 ^a	3	300 mg
2	3	600 mg
3	3	1000 mg
4	3	1400 mg
5	3	2000 mg

These total daily dose levels may be evaluated in QD or BID dose schedules, including intermediate dose levels, and in expansion of an existing dose level of up to 12 evaluable subjects following discussions between the Sponsor and the investigators, if supported by evolving safety, tolerability, PK, and pharmacodynamic data.

BID = twice daily, PK = pharmacokinetic, QD = once daily.

a: Planned starting dose level in QD schedule.

Refer to [Section 9.4.4.1](#) for details regarding the dose-escalation procedure.

The MTD is defined as the highest dose at which no more than 1 of 6 subjects experiences a DLT in the dose cohort. (Note that at least 6 subjects must be treated at the dose level potentially considered to be the MTD before that dose level can be considered the MTD). Therefore, if ≥ 2 subjects within a cohort experience a DLT and the previous dose level did not enroll 6 subjects, enrollment will move down to the previous dose level and continue until 6 subjects are enrolled, and the same guidelines for determining the MTD will be followed.

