The RP2D may not exceed the MTD and will be agreed upon by the SRC, based on an integrated evaluation of safety, tolerability, clinical benefit, PK, and pharmacodynamic data, for all dose levels tested. Clinically significant toxicities (eg, chronic Grade 2 toxicities) or AEs that meet the definition of dose limiting but occurring after C1 (dose-modifying events,

DME) may be considered when determining the RP2D. Once the MTD/RP2D is reached, at least 6 HCC subjects must be enrolled at the RP2D (regardless of the total number of subjects enrolled at that dose level) to proceed with dose expansion.

To be evaluable for a DLT, subjects must have completed safety assessments through predose on C2 Day 1 and must have received at least 17 of 21 (approximately 80%) study days within C1, unless due to a DLT. Subjects who discontinue from the study for reasons other than DLT before completing C1 are to be replaced. Subjects who experience toxicities meeting DLT criteria during C1 will be discontinued from treatment. In rare cases, an exemption to study discontinuation for a DLT in 1st cycle may be considered after discussion between the treating physician, Sponsor and study medical monitor. Subjects who experience toxicities meeting DLT criteria may, at the discretion of the investigator and after discussion with the Sponsor, be allowed to continue study drug at a reduced dose if this is judged to be in the best clinical interest of the subject. The Sponsor will communicate information about DLTs or safety concerns rapidly to all sites as per the separate Dose Escalation Plan, which also details the format and timelines of the Dose Escalation review meetings, and the communication of dose level decisions to all sites.

9.1.1.1.1 **DEFINITION OF DOSE-LIMITING TOXICITIES OR DOSE-MODIFYING EVENTS**

DLTs are defined as any of the toxicities listed in Table 2 occurring during C1 Phase 1 only and judged by the investigator as related to study drug (ie, assessed as unrelated to disease, intercurrent illness, or concomitant medications). Any event that occurs in C2 or beyond (including any cycle in Phase 2) will be considered a DME.

Table 2 Definition of Dose-Limiting Toxicity (Cycle 1 Phase 1 Only) or Dose-Modifying Event (Cycle 2 or Beyond and Any Cycle in Phase 2)

TOXICITY	CRITERIA

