9.4.4.1 Dose Escalation Scheme (Part 1)

The starting dose of H3B-6527 is 300 mg QD.

H3B-6527 doses will be escalated sequentially after the SRC, with appropriate representation from the Sponsor and participating investigators, reviews safety data collected during C1 from the subject(s) enrolled at the current dose level.

Subjects who do not receive study drug for at least 17 of 21 days (approximately 80%; not necessarily consecutively) during the first cycle for reasons not considered to be a DLT by both the investigators and the Sponsor will be replaced. The subjects who are replaced will not be considered evaluable for DLT assessments.

Based on the interim evaluation of the safety and tolerability data of the previous dose level, the Sponsor may decide to initiate accrual at an intermediate dose level. The SRC may be convened earlier at the discretion of the Sponsor if important safety issues arise requiring the attention of the committee.

Up to 3 subjects initially are to be enrolled. After 3 subjects complete C1 and have safety evaluations performed through C2 Day 1, and:

- None of these 3 subjects experience a DLT (see [Section 9.1.1.1.1](#)), then enrollment of the next cohort may commence with approval from the SRC.
- 1 of 3 subjects within a cohort experiences a DLT (see [Section 9.1.1.1.1](#)), then up to 3 additional subjects are to be enrolled sequentially at that dose level. If none of the

additional 3 subjects has a DLT (ie, 1 of 6 subjects has a DLT), then enrollment at the next scheduled dose may commence with approval from the SRC.

- If ≥ 2 subjects within a cohort experience a DLT (see [Section 9.1.1.1.1](#)), then the DLT dose level will have been reached and the previous lower dose level will be considered the MTD. Note that at least 6 subjects must be treated at the dose level potentially considered to be the MTD before that dose level can definitely be considered the MTD. Therefore, if ≥ 2 subjects within a cohort experience a DLT and the previous dose level did not enroll 6 subjects, enrollment will move down to the previous dose level and continue until 6 subjects are enrolled, and the same guidelines for determining the MTD will be followed.
 - Once the MTD or RP2D is established, additional subjects will be treated in the Expansion phase of the study (Part 2), which is designed to better characterize the safety, tolerability and preliminary antitumor activity of the study drug when provided at the RP2D and schedule.

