- Worsens in severity during treatment relative to the pretreatment state, when the AE is continuous.

Only those AEs that were treatment emergent will be included in summary tables. All AEs, treatment emergent or otherwise, will be presented in subject data listings.

The TEAEs will be summarized overall and by study part and cohort. The incidence of TEAEs will be reported as the number (percentage) of subjects with TEAEs by SOC and PT. A subject will be counted only once within a SOC and PT, even if the subject experienced more than 1 TEAE within a specific SOC and PT. The number (percentage) of subjects with TEAEs will also be summarized by maximum CTCAE grade.

The number (percentage) of subjects with TEAEs will also be summarized by relationship to study drug (Yes [related] and No [not related]).

The number (percentage) of subjects with TEAEs leading to death will be summarized by MedDRA SOC and PT overall and for each study part and cohort. A subject data listing of all AEs leading to death will be provided.

The number (percentage) of subjects with treatment-emergent SAEs will be summarized by MedDRA SOC and PT overall and for each study part and cohort. A subject data listing of all SAEs will be provided.

The number (percentage) of subjects with TEAEs leading to discontinuation from study drug will be summarized by MedDRA SOC and PT overall and for each study part and cohort. A subject data listing of all AEs leading to discontinuation from study drug will be provided.

In DLT-evaluable subjects, the number (percentage) of subjects with DLT will be presented by dose level for Dose Escalation phase of the study. Listing of subjects with DLT will be provided.

9.7.1.8.3 **LABORATORY VALUES**

Laboratory results will be summarized using Système International (SI) units, as appropriate. For all quantitative parameters listed in [Section 9.5.1.4.3](#), the actual value and the change from baseline to each postbaseline visit and to the end of treatment (defined as the last on-treatment value) will be summarized by visit and study part and dose cohort using descriptive statistics. Qualitative parameters listed in Section 9.5.1.4.3 will be summarized using frequencies (number and percentage of subjects), and changes from baseline to each postbaseline visit and to end of treatment will be reported using shift tables. Percentages will be based on the number of subjects with both nonmissing baseline and relevant postbaseline results.

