AE = adverse event, ALT = alanine aminotransferase, AST = aspartate aminotransferase, C = Cycle, CTCAE = Common Terminology Criteria for Adverse Events, ULN = upper limit of normal.

The MTD is defined as the highest dose at which no more than 1 of 6 subjects experiences a DLT in the dose cohort. (Note that at least 6 subjects must be treated at the dose level potentially considered to be the MTD before that dose level can be considered the MTD).

The RP2D may not exceed the MTD and will be agreed upon by the SRC based on an integrated evaluation of safety, tolerability, clinical benefit, PK, and pharmacodynamic data, for all dose levels tested. Clinically significant toxicities (eg, chronic Grade 2 toxicities) or adverse events (AEs) that meet the definition of dose limiting but occurring after C1 (dose modifying events, DME) may be considered when determining the RP2D. Once the MTD/RP2D is reached, at least 6 HCC subjects must be enrolled at the RP2D (regardless of the total number of subjects enrolled at that dose level) in order to proceed with dose expansion.

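### Part 1 was dosed first fasted and then with food, but the intrapatient-escalation rule and the DLT and PK tables do not name food state

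*SAP*

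**What the plan says.** **Food state.** The protocol's amendment history, used here only as a record of how earlier subjects were dosed, shows that Amendment 08 removed a fasting requirement (2 hours before and 2 hours after dose) from Table 6, the Dose Escalation schedule. Subjects had been enrolled before then: SAP 3.2.2 records ICC subjects entering between Amendments 5 and 7. Protocol 9.1, 9.4.6 and Table 6 footnote y now give drug with a meal. Protocol 9.1 and 9.2 cap the fed starting dose at half of the total daily dose previously found safe and send further escalation back to Section 9.1.1. That cap is the only food-specific dose rule. SAP 3.2.1 says dosing is with food in both parts and does not mention fasted cohorts.

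**Escalation rules.** Protocol 9.1.1.1 separates decisions by schedule: "decisions regarding dose escalation will be made based on review of data from subjects enrolled in cohorts on the same schedule". After Cycle 3, an eligible subject may escalate to the highest level that has completed DLT assessment within the same schedule and was safe (no DLT in the first 3, or at most 1 in 6).

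**Six-subject minimums.** SAP 3.2.2 requires that "at least 6 subjects must be treated at the dose level potentially considered to be the MTD". Protocol 9.1.1.1 adds that "at least 6 HCC subjects must be enrolled at the RP2D". If a level fails and the one below has fewer than six subjects, "enrollment will move down to the previous dose level and continue until 6 subjects are enrolled".

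**Tables.** SAP 5.6.2 states: "To assess the MTD and DLT, the number (percentage) of subjects with DLT events in each dose level will be summarized". Protocol 9.7.1.8.2 agrees: "In DLT-evaluable subjects, the number (percentage) of subjects with DLT will be presented by dose level for Dose Escalation phase of the study". SAP 5.5 tabulates PK by dose level, day and time. SAP 5 breaks Part 1 outputs down by dose cohort, but SAP Table 1 identifies its levels only by total daily dose.

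**The concern.** By halving the restart dose, the sponsor treated a given number of milligrams with food as not equivalent, for safety, to the same number fasted. The rules that clear doses and the tables that report them do not carry that distinction.

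- **Intrapatient escalation.** A fed subject can be sent to a level that only fasted subjects have cleared. This needs no fed cohort at that dose. Protocol 9.1.1.1 also leaves such subjects out of the DLT analysis at the higher level, so the first fed exposures there could fall outside the DLT count.
- **Reporting.** Where a nominal dose was given both ways, one DLT rate and one PK summary would average two dosing conditions. Part 2 is fed, so the fed figures are the ones that matter for the MTD and RP2D.
- **Counting.** The six-subject minimums do not say whether earlier fasted subjects at the same nominal dose count.

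**Working it through.** **1. The plan's own figure.** There is no figure on food state. The nearest is the Part 1 size: 5 QD levels × 6 = 30, and (5 + 3) levels × 6 = 48. This matches the stated 30 to 48. The calculation has no separate allowance for repeating a level with food.

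**2. Size of the intrapatient step.** Let D be the fasted dose that set the cap, and assume it was also the highest cleared level on the subject's schedule. The fed start s satisfies s ≤ D/2, so the step to D is D/s ≥ 2.

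- Planned steps (Protocol Table 1): 150→300 and 300→600 are 2.00; 600→1000 is 1.67; 1000→1400 is 1.40; 1400→2000 is 1.43.
- Fed start exactly at D/2: 2.00 for every D. This equals the two lowest planned steps and exceeds the other three.
- Fed start limited to Table 1 levels: for D = 300, 600, 1000, 1400 and 2000 the highest permitted start is 150, 300, 300, 600 and 1000. The steps are 2.00, 2.00, 3.33, 2.33 and 2.00.

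A subject who entered a later, higher fed cohort would face a smaller step.

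**3. Can nominal doses overlap?** If D = 2000 mg, the cap is 1000 mg, and fed re-escalation on Table 1 levels can revisit 1000, 1400 and 2000 mg. If D = 1000 mg, the cap is 500 mg, and 300, 600 and 1000 mg can recur. Overlap is not certain. The fed start is not given, and under Protocol 9.4.4.1 "the Sponsor may decide to initiate accrual at an intermediate dose level".

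**4. The six-subject count.** A fed cohort with 1 DLT in 3 must be expanded with new subjects: "up to 3 additional subjects are to be enrolled sequentially at that dose level". Only a clean 0/3 fed cohort could therefore be completed with fasted subjects. A fasted level cleared on exactly three subjects must itself have been 0/3, so the top-up cannot fail and the fasted DLT rate drops out. With assumed fed DLT rate p:

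- Fasted top-up: P = (1−p)³ + 3p(1−p)² × (1−p)³
- Six fed subjects: P(≤1 of 6) = (1−p)⁶ + 6p(1−p)⁵

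| p (assumed) | P(0/3) | P(1/3) | Top-up | Six fed | Difference (unrounded inputs) |
|---|---|---|---|---|---|
| 10% | 0.729 | 0.243 | 0.906 | 0.886 | 0.020 |
| 20% | 0.512 | 0.384 | 0.709 | 0.655 | 0.053 |
| 30% | 0.343 | 0.441 | 0.494 | 0.420 | 0.074 |
| 40% | 0.216 | 0.432 | 0.309 | 0.233 | 0.076 |

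For example, at 30%: 0.343 + 0.441 × 0.343 = 0.494. The difference is P(0/3) × P(at least 2 of the next 3): 0.343 × 0.216 = 0.074. These are pass probabilities for one level, not for the final MTD choice, which also depends on the next level failing.

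**The case against.** The best defence is that fed dosing was a new escalation sequence. It restarted low under Section 9.1.1, the MTD definition speaks of the dose cohort, and a halved restart would serve little purpose if fasted subjects counted towards clearance. On that reading the level below means the previous fed cohort. This is the more natural reading and it largely stands, so a reader should not infer that a fed MTD will in fact rest on fasted subjects. The text only fails to exclude it.

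A second defence is that dose level cannot be an exhaustive list of strata, since taken literally it would also pool QD with BID. The separate PK plan, the table shells and the Dose Escalation Plan may already split by food state, and Figure 1 is not available. That limits the reporting point to what these two documents say. It does not answer it, because SAP 3.2.1 gives a programmer no sign that fasted cohorts exist.

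Third, intrapatient escalation requires three completed cycles, no progression, no drug-related reduction or interruption, and agreement of the investigator and medical monitor. These are real safeguards, but they leave the target dose as written.

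Two stronger inferences fail. One is to pool three fed with three fasted subjects freely, which at assumed rates of 33% and 10% gives 0.616 against 0.358 for six fed. The 3+3 rule forbids this, because 1/3 fed triggers new enrolment. The other is that the BID start is unprotected. The cap is worded by total daily dose, not by QD, so it can cover a fed BID start.

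**Conclusion.** The point holds in a limited form. The intrapatient rule is the firmest part: as written it permits a fed subject to go to a level cleared only fasted, at least a 2-fold step from a first fed dose within the cap, with no nominal overlap needed. The DLT and PK tables would mix food states wherever a nominal dose was given both ways; overlap is plausible but unproven, and unavailable documents may already deal with it. The six-subject count is a secondary ambiguity, worth about 5 to 8 percentage points in the chance of passing at fed DLT rates of 20% to 40%. Those rates are assumptions. The documents give neither a fed/fasted exposure ratio nor DLT rates by food state, so no PK effect can be sized. The SRC's integrated judgement on the RP2D lowers the risk without changing the rules.

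**What to change.** - **SAP 5, 5.5 and 5.6.2:** define the Part 1 dose cohort as total daily dose × schedule × food state, and give the DLT, TEAE and PK tables by that cohort.
- **SAP 3.2.1:** state that earlier cohorts were dosed fasted.
- **Protocol 9.1.1.1:** require the intrapatient target to have been cleared in the fed state.
- **Protocol 9.1.1.1 and 9.4.4.1:** state that the six-subject MTD/RP2D count, including the step-down rule, means fed DLT-evaluable subjects.
- **BID:** state only that the one-half cap also applies to a fed BID start.

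The cost is SAP wording, extra table columns with smaller denominators, and a short protocol clarification. Up to three more fed subjects might be needed at the chosen dose, and only if fasted subjects would otherwise have been counted. No new procedures are required.
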